12.2 Analysis Sets

Safety set: all randomised subjects who receive a dose of study treatment, including partial dose.

PK set: all subjects from the safety population excluding subjects without any valid PK measurement or with important protocol deviations significantly affecting PK, for example, use of non-permitted medications. Exact definition of important protocol deviations significantly affecting PK will be discussed by the clinical team and described in a specific

Clinical Study Code No.: CLI-10067AA1-01	Version No.: 6.0
EUDRACT No.: 2022-001079-15	Date: 06 July 2023

document before bioanalytical data are disclosed. Subjects will not be excluded on the basis of statistical analysis or for PK reasons, except in the cases defined in the European Medicine Agency guideline [24].

After unblinding, subjects will not be excluded on the basis of statistical or for PK reasons, except in the case of:

- non-zero baseline concentration $> 5\%$ of C_{\max}
- AUC_{0-t} lower than 5% of the reference medicinal product geometric mean of AUC_{0-t} (calculated without inclusion of data from the outlying subject)
- below the limit of quantification concentration at all timepoints.

Pharmacokinetic variables will be analysed in the PK set. The safety set will be used in the analysis of all safety variables. In case of deviation between randomised treatment and treatment actually received, the treatment actually received will be used (i.e., an as-treated analysis will be performed).

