2. PHARMACOKINETIC, AND IMMUNOGENICITY ANALYSES

2.1 PHARMACOKINETIC ANALYSES

2.1.1 Available data

Blood samples will be collected for the determination of CHF10067 in serum at the following time points: pre-dose (within 75 minutes from start of infusion), at the end of infusion, and 2, 4, 8, and 20 hours after the end of the infusion and 5, 7, 14, 28, 56 and 84 days post-dose.

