2.1.2 Endpoints and derivation rules

The following PK parameters will be derived for serum CHF10067:

- AUC_{0-t} , AUC_{inf} , C_{max} , t_{max} , C_{inf} , t_{inf} , CL , V_z , $t_{1/2}$.

Standard non-compartmental methods will be used for the calculation of the PK parameters from the individual serum concentration – time profiles using actual sampling time points from start of infusion. If actual sampling time is not available, nominal time will be used (see also section 6.1.3.1). The analysis will consider time only in hours and minutes. Any seconds in the time part of a record will be imputed by zero. The area under the serum concentration-time curve (AUC) will be calculated according to the linear trapezoidal method.

PK parameters definition

- AUC_{0-t} : AUC from 0 to the last quantifiable concentration;
- AUC_{inf} : AUC from 0 to infinite time calculated as: AUC extrapolated to infinity will be calculated as the sum of AUC_{0-t} and a residual part extrapolated to infinite time. The residual area from the last concentration data point to infinite time is calculated using the approximation:

$$\int_t^{\infty} C_t dt = C_t / \lambda_z$$

where λ_z is the first order terminal rate constant, estimated by linear regression of the terminal loglinear segment of the plasma log concentration curve, and C_t is the last quantifiable concentration data point;

- C_{max} and t_{max} : the value and time of the maximum serum concentration will be obtained directly from the experimental data without interpolation;
- C_{inf} and t_{inf} : the value and time of the serum concentration at end of infusion;
- CL : clearance will be calculated as:

$$Dose / AUC_{inf}$$

- V_z : volume of distribution will be calculated as:

$$Dose / (\lambda_z * AUC_{inf})$$

	Statistical Analysis Plan	
CLI-10067AA1-01	Final Analysis	Final 1.0 of 30MAY2024

- $t_{1/2}$: terminal half-life, associated with negative slope ($-\lambda z$), will be calculated as $0.693/\lambda z$ from the individual drug concentration time profiles

Criteria for $t_{1/2}$ estimation

- At least three time points (excluding t_{max}) should be used for the determination of the elimination rate constant (λz), otherwise the $t_{1/2}$ as well as the derived parameters (AUC_{inf} , CL and Vz) cannot be estimated and will be presented as “NE” (not estimated) in the tables.

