- The adjusted correlation coefficient of the linear regression should be ≥ 0.85 , otherwise the $t_{1/2}$ as well as the derived parameters (AUC_{inf} , CL and Vz) are not reliably estimated and will not be reported (presented as “NR” (not reported) in the tables).

Criteria for AUC_{inf} estimation

- When for a profile the $AUC_{extrapolated} / AUC_{0-\infty} > 20\%$, this AUC_{inf} as well as the derived parameters (CL and Vz) will be excluded from the statistical analyses.

All PK parameters will be estimated, if feasible, and presented in the TLFs, unless specified differently (e.g., unreliable $t_{1/2}$). PK parameters that cannot be estimated will be specified in the Data Review Report (DRR) (*prior* to database lock and disclosure of the bioanalytical data) and/or PK DRR (*after* database lock and disclosure of the bioanalytical data). PK data that is excluded from PK analysis will be discussed in the DRR and/or PK DRR, and marked in the relevant tables, accompanied with a footnote.

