2.1.3 Inferential statistics

Dose proportionality in terms of CHF10067 AUC_{0-t} , AUC_{inf} , and C_{max} will be evaluated using the power model, including the log-transformed PK parameters as dependent variables, and the log-transformed CHF10067 dose as a covariate. The slope for log-transformed dose will be estimated with its 90% confidence interval (CI) to examine dose proportionality.

There will be no evidence for deviation of dose proportionality in case the 90% CI of the fixed slope for log-dose contains 1.

SAS code is provided in section 10.1.

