2.1.4 Presentation of results

Listing

The actual sampling date/time and the actual time of end of infusion will be listed per subject, dose level and analysis time point. For samples that are reallocated to another analysis time point window, the new analysis time point window will be presented in “Analysis Time Window” column. Additionally, individual PK concentrations will be presented. PK concentrations excluded from PK parameter estimation and/or descriptive statistics will be marked and clarified with a remark. Important time deviations will be reported with elapsed time from planned timepoint in “Remarks” column.

	Statistical Analysis Plan	
CLI-10067AA1-01	Final Analysis	Final 1.0 of 30MAY2024

Subjects that are excluded from the PK set and/or PK data that is excluded from PK parameter estimation, descriptive statistics and/or inferential statistics will be listed per subject, dose level and concentration time point or PK parameter, with the reason for exclusion. If this reason is due to an important protocol deviation, it will be marked too.

Tables

Individual actual sampling time points relative to end of infusion will be tabulated, per dose level. Important time deviations will be marked in the table with appropriate footnoting. Missing sampling times will be reported as “NT” (no time). Missing samples will be reported as “NS” (no sample).

Individual serum concentration data together with descriptive statistics will be tabulated, per dose level at each allocated analysis time point window. A footnote will be added to specify that a time windowing approach was considered to assign samples to the analysis time point. Missing samples or samples missing in an analysis time point window due to reallocated to another analysis time point window will be reported as “NRS” (no sample or reallocated sample). Samples for which no result is available will be reported as “NR” (no result). Exclusion of PK concentrations from descriptive statistics is described in section 6.1.3.1.

Individual PK parameters together with descriptive statistics will be tabulated, per dose level. Not estimable PK parameters will be reported as “NE” (not estimated). Exclusion of PK parameters from descriptive statistics is described in section 2.1.2 and section 6.1.3.1.

For the dose proportionality assessment on CHF10067 AUC_{0-t}, AUC_{inf}, and C_{max}, the slope and 90% CI of the power model will be tabulated.

Figures

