6.4.4 Raw SAS output

In addition to the statistical output as described in section 9, raw SAS output will be delivered in separate files as ‘Appendix to Table 14.x.x.x’ for all tables presenting inferential statistics. The layout of the appendices will be similar to the table (study identifier, SAS program name, production date, page count); presenting the raw SAS output in the body section.

6.4.5 eCTD tables

Additional tables will be delivered in separate files as ‘Appendix to Table 14.x.x.x’ for all tables presenting PK parameters: they will be created separately for each

Statistical Analysis Plan

CLI-10067AA1-01

Final Analysis

Final 1.0 of 30MAY2024

analyte and will present the subjects/profiles (if any), per treatment, showing $AUC_{0-t}/AUC_{0-\infty} < 0.8$, C_{max} as the first point and pre-dose sample $> 5\% C_{max}$ per treatment.

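### The 20% extrapolation rule in SAP 2.1.2 removes long-half-life profiles from the AUCinf, CL and Vz analyses, and no analysis that includes them is planned

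*SAP*

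**What the plan says.** SAP 2.1.2 has two layers of criteria. The first concerns the terminal slope: at least three points, and an adjusted correlation of at least 0.85. The second applies to profiles that pass the first. If the extrapolated share exceeds 20%, AUCinf "as well as the derived parameters (CL and Vz) will be excluded from the statistical analyses".

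SAP 2.1.4 carries the rule into the summary tables: "Exclusion of PK parameters from descriptive statistics is described in section 2.1.2 and section 6.1.3.1". It also limits the dose-proportionality plot to values used in the analysis.

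Dose proportionality of AUC0-t, AUCinf and Cmax is assessed "using the power model, including the log-transformed PK parameters as dependent variables, and the log-transformed CHF10067 dose as a covariate" (SAP 2.1.3). The reading rule is: "There will be no evidence for deviation of dose proportionality in case the 90% CI of the fixed slope for log-dose contains 1". The 20% rule touches AUCinf only; AUC0-t, Cmax and half-life are kept.

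Neither document plans an AUCinf, CL or Vz analysis that includes the excluded profiles.

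**The concern.** Sampling stops at the same planned day for everyone. A large extrapolated share therefore marks a half-life that is long relative to the last sample. Half-life is proportional to V/CL and AUCinf equals dose/CL, so the profiles removed tend to have low CL and high AUCinf. The filter acts on the quantity being analysed.

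Two consequences follow if half-lives are long enough. The CL summary is too high and the AUCinf summary too low at each dose, even under exact proportionality. And if clearance falls as dose rises, the higher-dose cohorts lose more profiles, which pulls the AUCinf slope towards 1, the value that the SAP reads as no evidence of deviation. Protocol 1.2 says that the PK data will help to choose doses for later studies, so a CL mean or AUCinf slope shaped by this filter should not be the only one reported.

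**Working it through.** The plan states no half-life, variability or power for these models, so there is no figure of its own to reproduce.

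**Inputs from the documents**
- Sampling: end of infusion, then "2, 4, 8, and 20 hours after the end of the infusion and 5, 7, 14, 28, 56 and 84 days post-dose" (SAP 2.1.1).
- AUC "will be calculated according to the linear trapezoidal method" (SAP 2.1.2).
- Six subjects on active drug at each of 1000, 2000 and 3000 mg (SAP 1.3 and 10.1).
- 90% CI for the slope (SAP 2.1.3).

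**Assumptions**
- Mono-exponential decline.
- Median half-life at 1000 mg between 14 and 32 days.
- SD of log CL 0.3 and SD of log V 0.15.
- 10% assay error, and terminal slope from the last three points.
- CL proportional to dose^-(slope − 1).
- 3000 simulated trials per setting.

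**Step 1: half-life at which the rule applies.** With last sample at time T, the extrapolated share is exp(−λz·T). It exceeds 0.2 when t½ > T·ln2/ln5 = 0.431·T.
- T = 84 days: 36.2 days (36.0 using the linear trapezoid at the planned times)
- T = 56 days: 24.1 days
- T = 28 days: 12.1 days

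**Step 2: who is lost.** Take a half-life of 25 days at 1000 mg and a true slope of 1.25. Median half-life is 25 × 2^0.25 = 29.7 days at 2000 mg and 25 × 3^0.25 = 32.9 days at 3000 mg. The SD of log half-life is √(0.3² + 0.15²) = 0.335. The share above 36.2 days is 1 − Φ[ln(36.2/median)/0.335]:
- 1000 mg: 1 − Φ(1.10), about 13–14%
- 2000 mg: 1 − Φ(0.59), about 28%
- 3000 mg: 1 − Φ(0.285), about 39%

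Simulation gives 14%, 26% and 34%. It is lower at the top dose because some long-half-life profiles fail the terminal-slope check first and are out of both analyses. The expected loss is 6 × (0.14 + 0.26 + 0.34) = 4.4 of 18 profiles.

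**Step 3: bias in CL when the true slope is 1.** Losses are equal across doses, the mean slope stays at 1.00 and rejection stays near 10%. Geometric mean CL, kept profiles over all profiles, is 1.00 at 14 days, 1.03 at 21 days and about 1.10 at 28 days.

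**Step 4: the AUCinf slope when CL falls with dose.** At 25 days and true slope 1.25, the mean slope is 1.24 with all acceptable profiles and 1.17 after the filter. The chance that the 90% CI excludes 1, with complete Day 84 sampling:

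| True slope | Half-life at 1000 mg | AUCinf, all | AUCinf, filtered | AUC0-t |
|---|---|---|---|---|
| 1.25 | 14 d | 44% | 43% | not tabulated |
| 1.25 | 21 d | 44% | 34% | 43% |
| 1.25 | 25 d | 42–44% | 27–30% | 42–43% |
| 1.25 | 28 d | 43% | 22% | 42% |
| 1.25 | 32 d | 39% | 18% | 39% |
| 1.4 | 21 d | 76% | 55% | 76% |
| 1.4 | 25 d | 75% | 40% | 73% |
| 1.4 | 28 d | 73% | 29% | 72% |

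Ranges are across repeat runs.

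**Step 5: how far AUC0-t helps.** Its slope is attenuated too (about 1.17 at 25 days for a true 1.25), but its CI is narrower, so with complete sampling it detects about as often as unfiltered AUCinf. With 15% of profiles cut short, at 25 days and slope 1.25, AUC0-t falls to 24–30%, against 38–41% for unfiltered AUCinf. The result varies with how the profiles are cut.

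**The case against.** The strongest counter-argument is that the plan already covers most of this. The same power model and reading rule apply to AUC0-t, which the filter does not touch, and the table bears this out under complete sampling. Half-life stays in the by-dose summary, so half-life lengthening with dose would be visible. Individual values are still presented. Exclusions are footnoted and listed with reasons (Listing 16.2.5.3), and the SAP 6.4.5 appendix tables "analyte and will present the subjects/profiles (if any), per treatment, showing" an AUC0-t to AUCinf ratio below 0.8. This is a secondary objective with six subjects per dose. The slope shift of 1.24 − 1.17 = 0.07 is small beside a CI half-width of about 0.26.

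All of that stands. It does not supply a CL, Vz or AUCinf summary that includes the excluded profiles, nor say what to conclude if AUC0-t and filtered AUCinf disagree.

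A reader might draw stronger conclusions that the documents do not support:
- *That the rule hides more-than-proportional exposure.* With complete sampling the AUC0-t model would detect it about as often as unfiltered AUCinf.
- *That the analyses describe only fast clearers.* The rule acts on half-life relative to the last sample. A large V, early withdrawal or missed late sample also triggers it. At an assumed 28 days, roughly four-fifths or more of excluded subjects have below-median CL, but only about half to two-thirds belong to the equally sized slowest-CL group. With half-lives well under 36 days and complete sampling, almost no one is dropped.
- *That the SAP breaches the protocol.* Protocol 12.2 says "Subjects will not be excluded on the basis of statistical analysis or for PK reasons, except in the cases defined in the European Medicine Agency" (meaning its bioequivalence guideline), but that concerns removing subjects from the PK set. Here the subject stays and a parameter is set aside. SAP 6.1.3.1 points to 2.1.2 for parameter criteria, and Protocol 12.3 leaves detail to the SAP.
- *That flagged values should simply become the main analysis.* The simulation assumes mono-exponential decline, which makes extrapolation correct by construction. It cannot show that an AUCinf resting largely on a three-point tail is safe.

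**Conclusion.** The concern holds in a conditional form. The exclusion is informative, and it is applied on top of a terminal-slope check that the profile has already passed. From about 21 days' half-life upward, CL is overstated by about 3% (21 days) to 10% (28 days) even under proportionality. A true AUCinf slope of 1.25 at 25 days is estimated at about 1.17, with detection falling from about 42% to 27–30%. At 14 days nothing material happens.

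These sizes rest on assumed half-lives and variability and on mono-exponential decline. The Day 84 threshold of about 36 days needs only the last of these. Sampling times were chosen from healthy-subject results, and Protocol 7.2.1.2 allows for different PK in IPF, so a short half-life cannot be taken for granted. The AUC0-t model limits the harm to the proportionality conclusion but does not help CL or Vz. The gap is the missing parallel analysis.

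**What to change.** Keep the 20% flag and the restricted analysis. Add to SAP 2.1.2–2.1.4:

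- The AUCinf power model and the AUCinf, CL and Vz summaries are also presented with all flagged profiles that meet the terminal-slope criteria, beside the restricted version.
- The number of flagged profiles per dose level is shown next to each slope.
- Flagged points appear on the dose-proportionality plot with a distinct symbol.
- A restricted 90% CI that contains 1 is not read as no evidence of deviation when the two analyses disagree or when exclusions differ by dose.

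The cost is SAP wording and one repeated table. No new data are needed, and SAP 6.4.5 already identifies the profiles. The downside is that flagged values lean more on the extrapolated tail, which is why they belong in a parallel analysis with the restricted one kept beside it.

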2.1.3 Inferential statistics

Dose proportionality in terms of CHF10067 AUC_{0-t} , AUC_{inf} , and C_{max} will be evaluated using the power model, including the log-transformed PK parameters as dependent variables, and the log-transformed CHF10067 dose as a covariate. The slope for log-transformed dose will be estimated with its 90% confidence interval (CI) to examine dose proportionality.

There will be no evidence for deviation of dose proportionality in case the 90% CI of the fixed slope for log-dose contains 1.

SAS code is provided in section 10.1.

2.1.4 Presentation of results

Listing

The actual sampling date/time and the actual time of end of infusion will be listed per subject, dose level and analysis time point. For samples that are reallocated to another analysis time point window, the new analysis time point window will be presented in “Analysis Time Window” column. Additionally, individual PK concentrations will be presented. PK concentrations excluded from PK parameter estimation and/or descriptive statistics will be marked and clarified with a remark. Important time deviations will be reported with elapsed time from planned timepoint in “Remarks” column.

	Statistical Analysis Plan	
CLI-10067AA1-01	Final Analysis	Final 1.0 of 30MAY2024

Subjects that are excluded from the PK set and/or PK data that is excluded from PK parameter estimation, descriptive statistics and/or inferential statistics will be listed per subject, dose level and concentration time point or PK parameter, with the reason for exclusion. If this reason is due to an important protocol deviation, it will be marked too.

Tables

Individual actual sampling time points relative to end of infusion will be tabulated, per dose level. Important time deviations will be marked in the table with appropriate footnoting. Missing sampling times will be reported as “NT” (no time). Missing samples will be reported as “NS” (no sample).

Individual serum concentration data together with descriptive statistics will be tabulated, per dose level at each allocated analysis time point window. A footnote will be added to specify that a time windowing approach was considered to assign samples to the analysis time point. Missing samples or samples missing in an analysis time point window due to reallocated to another analysis time point window will be reported as “NRS” (no sample or reallocated sample). Samples for which no result is available will be reported as “NR” (no result). Exclusion of PK concentrations from descriptive statistics is described in section 6.1.3.1.

Individual PK parameters together with descriptive statistics will be tabulated, per dose level. Not estimable PK parameters will be reported as “NE” (not estimated). Exclusion of PK parameters from descriptive statistics is described in section 2.1.2 and section 6.1.3.1.

For the dose proportionality assessment on CHF10067 AUC_{0-t}, AUC_{inf}, and C_{max}, the slope and 90% CI of the power model will be tabulated.

Figures

Serum concentration - time profiles will be presented in linear/linear and log/linear scales. Mean (\pm SD for linear/linear scale) graphs will be presented with all dose levels on the same graph. Individual graphs will be presented per dose level, with all subjects on the same graph. The graphs will be presented over the full-time scale (i.e., up to Day 84).

The following attributes will be used in the concentration – time profiles:

- Dose levels (mean graphs)
 - o A different colour, line pattern and symbol per dose level.
- Subjects (individual graphs with all subjects on the same graph, i.e., spaghetti plot)
 - o A different line pattern and symbol per subject, and a unique colour for ADA positivity or negativity (see definitions in Section 2.2.2).

The individual and geometric mean values (log-transformed) of CHF10067 AUC_{0-t}, AUC_{inf}, and C_{max} will be presented graphically versus log-transformed dose. In addition, the linear regression line fitted will be displayed on each plot. The individual values will have the same colour and symbol as used in the concentration – time profiles. Only individual values used in the analysis will be plotted.

2.2 IMMUNOGENICITY

2.2.1 *Available data*

Serum samples for anti-drug antibody (ADA) assessments will be conducted utilizing a tiered approach (i.e., screen, confirm, titer), and ADA data will be collected pre-dose and at Days 14, 28, 56, and 84 and in case of early termination visit.

[figure not shown]
ADA result from each sample will be reported as either:

- ADA-positive: when ADA is detected at both screening and confirmatory tests in a sample, the sample is considered positive.
- ADA-negative: when ADA is not detected at screening test OR ADA is detected at screening but not detected at confirmatory test, the sample is considered negative.
- ADA-unevaluable: when a sample could not be tested for ADA status (“un-assayed sample”) due to inadequate sample volume, mishandling, or errors in sample collection, processing, storage, etc., either at screening or confirmatory test.

If the confirmatory sample is positive (i.e., ADA-positive sample), the ADA titer will be reported as well. ADA titer is a quasi-quantitative expression of the level of ADA in the sample.

In addition, the presence of neutralizing antibody (nAb) will be tested for all ADA -positive samples using a ligand-binding assay. The nAb results will be reported as either positive or negative.

ADA sample results

2.2.2 *Derivation rules*

No data imputation will be performed for missing and/or unevaluable samples.

Using the sample ADA status, subjects will be classified using the following definitions:

- **ADA evaluable subject**: A subject with baseline sample and at least one sample taken after drug administration during the treatment periods that are appropriate for ADA testing (i.e., with reportable result).
- **ADA unevaluable subject**: A subject without an evaluable sample at baseline OR with reportable baseline result but without a single sample taken (or without a reportable result) after drug administration during the treatment period.
- **ADA-positive subject (ADA+)**: A subject with at least one treatment-induced or treatment-boosted ADA-positive sample at any time during the treatment period. See definitions of treatment-induced and treatment-boosted ADA in Section 2.2.3.
- **ADA-negative subject (ADA-)**: A subject without a treatment-induced or treatment-boosted ADA-positive sample during the treatment period.

2.2.3 *Presentation of results*

The number and percentage of subjects who fulfil the below criteria will be presented by treatment.

- **Baseline ADA-positive**
For this group of subjects, titer range (median and interquartile range (IQR)) of the baseline ADA-positive samples will be reported.
- **ADA positive at any visit (ADA prevalence)**
A subject with at least one positive ADA result available at any time, including baseline (i.e., pre-existing ADA) and post-baseline measurements (i.e., ADA+). For this group of subjects, peak positive titer and range (median, IQR) will be reported.
- **ADA incidence**
 - **Treatment-induced ADA**, defined as ADA developed de novo (seroconversion) following drug administration (i.e., formation of positive ADA any time after the drug administration in subjects with ADA-negative baseline).
For this group of subjects, the following additional parameters will be presented:
 - Peak positive titer and range (median, IQR);
 - **Onset of ADA**
Time to onset of ADA (i.e., time period between the initial administration of the drug and the first instance of treatment-induced ADA);
 - **Duration of ADA**
 - **Persistently positive ADA**
Subjects having a treatment-induced ADA detected at

least two non-consecutive time points, with the last ADA-positive measurement (irrespective of any negative samples in between first and last positive measurements) being detected at the end of the study period (i.e., day 84) for completer subjects or at the last available sampling time point for prematurely discontinued subjects.

- *Transiently positive ADA*

Subjects having a treatment-induced ADA not fulfilling the above condition for persistently positive.

- Treatment-boosted ADA, defined as a baseline positive ADA titer (i.e., pre-existing ADA) that was boosted to a 4-fold or higher level following drug administration.

For this group of subjects, the fold increase in titer (ratio of peak post-administration titer to baseline titer) and range of titer increases (median, IQR) will be presented.

The combination of both treatment-induced and treatment-boosted ADA (i.e., the percentage of patients fulfilling this criterion) is defined as ADA incidence.

- nAb positive at any visit (including baseline and all post-baseline measurements).

All immunogenicity data will be listed.

Only if immunogenicity data will allow (i.e., if the number of ADA+ subjects will be ≥ 3), the effect of immunogenicity on PK and safety will be evaluated:

- **PK:** Serum concentration/time curves will be presented in linear/linear and log/linear scale. Plots will be presented by dose level and subject ADA status (i.e., ADA+ or ADA-), based on arithmetic means;
- **Safety:** The number and percentage of patients with treatment-emergent AEs will be summarized by subject ADA status (i.e., ADA+ or ADA-), in line with the summary reported in Section 3.1.3.

